13.2 IDENTIFYING AEs AND ARs

All AEs and ARs will be identified from the time a participant signs the consent form to take part in the study until the completion of study follow-up.

13.3 RECORDING AEs AND ARs

All AEs, including post-operative complications, and mortality, will be recorded as part of the outcome measures in the study CRF. There is no requirement to complete an additional AE form.

13.4 Detecting adverse events

Participants will be asked about the occurrence of AEs/SAEs at every visit during the study. Open-ended and non-leading verbal questioning of the participant will be used to enquire about AE/SAE occurrence. Participants will also be asked if they have been admitted to hospital, had any accidents, used any new medicines or changed concomitant medication regimens. If there is any doubt as to whether a clinical observation is an AE, the event will be recorded.

13.5 Assessment of causality

Should an AE or SAE occur the investigator will be asked to assess whether the event is related to the supplement and categorised as follows

Unrelated: Where the event is not considered to be related to the study supplement

Possibly Related: where the event is thought to be related to supplement based on a temporal relationship between administration of the supplement and occurrence of the event

Probably Related: Where the event is thought to be related to the supplement

13.5 Assessment of severity

Should adverse events occur that are thought to be possibly related or probably related to the supplement, the investigator will be asked to grade the severity as follows:

- Mild: an event that causes minimal discomfort and does not interfere with every day activities.
- Moderate: an event that is sufficiently discomforting to interfere with normal everyday activities.
- Severe: an event that prevents the participant undertaking normal everyday activities.

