13. ADVERSE EVENTS

The Investigator, or a delegated researcher, is responsible for the detection and documentation of adverse events that may be related to participating in the study and that meet the criteria and definitions detailed below.

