13.1 DEFINITIONS

An adverse event (AE) is an untoward medical occurrence in a study participant.

An adverse reaction (AR), in the context of this study, is any untoward and unintended response which is related to probiotics or dietary calcium supplements administered to that participant.

A serious adverse reaction (SAR) is any AR that:

- results in death of the clinical trial participant; is life threatening. A life-threatening AR refers to an event where the participant was at risk of death at the time of the event. It does not refer to an event which hypothetically might have caused death if it were more severe.
- requires in-patient hospitalisation[^] or prolongation of existing hospitalisation;
- results in persistent or significant disability or incapacity;
- consists of a congenital anomaly or birth defect;
- results in any other significant medical event not meeting the criteria above.

A suspected unexpected serious adverse reaction (SUSAR) is any AR that is classified as serious and is suspected to be caused by administration of the probiotics or dietary calcium supplements

[^]Any hospitalisation that was planned prior to randomisation will not meet seriousness criteria. Any hospitalisation that is planned post randomisation will meet the seriousness criteria unless it does not constitute an untoward medical occurrence (such as cosmetic elective surgery, social and/or convenience admission).

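### Severity is requested only for adverse events judged related, so moderate or severe events cannot be compared between arms free of that judgement

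*Protocol*

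**What the plan says.** The rules on adverse events are in Protocol section 13.

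- **Recording (13.3):** "All AEs, including post-operative complications, and mortality, will be recorded as part of the outcome measures in the study CRF". The same section adds: "There is no requirement to complete an additional AE form".
- **Causality (13.5 Assessment of causality):** "Should an AE or SAE occur the investigator will be asked to assess whether the event is related to the supplement". There are three classes: unrelated, possibly related and probably related. The first is defined as "Unrelated: Where the event is not considered to be related to the study supplement".
- **Severity (13.5 Assessment of severity; the number 13.5 is used twice):** a mild, moderate or severe grade is requested for events "thought to be possibly related or probably related to the supplement, the investigator will be asked to grade the severity".
- **Seriousness (13.1):** the criteria are introduced by "A serious adverse reaction (SAR) is any AR that", and an adverse reaction "is any untoward and unintended response which is related to probiotics or dietary calcium supplements administered to that participant".
- **Opening sentence of section 13:** the investigator's duty to detect and document is worded as covering "adverse events that may be related to participating in the study", which is narrower than the all-AE wording of 13.2 and 13.3.

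On presentation, section 4 describes probiotic and placebo as identical capsules, and calcium/vitamin D as a chewable tablet prescribed by the local study team.

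**The concern.** A severity grade describes what happened to the participant. Causality is an opinion about why it happened. When the opinion decides whether the description is collected, severity is missing according to a subjective judgement made after randomisation.

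Two things follow. First, any table of moderate or severe events by arm shows events that are both of that severity and judged related, not all such events. Second, if the readiness to call an event related differs by arm, the difference between arms in that table mixes a difference in events with a difference in attribution. The second risk is concrete here, because one active arm can be recognised by its tablet.

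This is a rule about what sites are asked to collect. A statistical analysis plan can choose how to tabulate severity, but it cannot by itself supply grades that sites were not asked to record.

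**Working it through.** The protocol gives no figure on this point, so there is none to reproduce. The check is a reading of the rules side by side, followed by what they imply for a count by arm.

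**1. Order of the two assessments.** Causality applies to every AE or SAE. Severity applies only to two of the three causality classes. Causality therefore has to be settled first, and the unrelated class leaves the process without a grade.

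**2. Whether another rule fills the gap.**

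| Place in the Protocol | What it asks for | Severity for unrelated AEs? |
|---|---|---|
| 8.2, 8.3 and the schedule of assessments | AEs recorded at 3 and 6 months | No |
| 13.1 | Seriousness criteria, for adverse reactions only | No; also depends on relatedness |
| 13.2 | All AEs and reactions identified from consent to end of follow-up | No |
| 13.3 | All AEs and deaths recorded; no additional form | No |
| 13.4 | Questions on events, admissions, accidents and medicines at each visit | No |
| 13.5 (severity) | Grade for possibly or probably related events | No |

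Seriousness is not a clear substitute. Its criteria are attached to reactions, and SAE is used in 13.4 and 13.5 without being defined.

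**3. What can be counted.** For one arm, write

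- S = all severe AEs;
- r = the share of those severe AEs judged possibly or probably related;
- U = the number of AEs judged unrelated, which are recorded but not graded.

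The severe count available from protocol-specified data is r × S. The all-cause severe count S is known only to lie between r × S and r × S + U.

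For two arms, 1 and 0, the ratio of available counts is

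(r1 × S1) / (r0 × S0) = (r1 / r0) × (S1 / S0).

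This equals the all-cause ratio S1 / S0 only if r1 = r0. The same holds for moderate events. By contrast, the count of all AEs per arm does not involve r, because section 13.3 records events whatever their cause.

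**4. Whether r can differ by arm.** The local team prescribes the calcium/vitamin D tablets (section 4) and capsule and tablet counts are made at the visits (8.2, 8.3), so allocation to that arm can be evident where causality is judged. In addition, the definition of a reaction names probiotics and calcium but not placebo, so the protocol leaves unclear how an event in the placebo arm comes to be classed as related. Neither point shows that r does differ; both show that nothing in the design holds it equal.

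**5. Size.** U and r depend on event rates and attribution habits that the protocol does not give. The possibly related class can be reached on timing alone, and dosing is daily for six months, so the share judged unrelated could be anywhere from small to large. No count of ungraded events is offered.

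**The case against.** The strongest reply is that little is lost. Sections 13.2 to 13.4 identify and record all AEs, ask at every visit about admissions, accidents and medicines, and record an event in case of doubt. All-cause AE counts, deaths and reported admissions can be compared by arm with no causality judgement. This stands. A reader might infer that harms nobody yet suspects would go unseen; the documents do not support that, since such events are recorded and only their grade is not requested.

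A second reply is that AE severity is not among the endpoints in section 5, and that with 25 participants per arm a severity table would be descriptive in any case. This also stands, and it limits the weight of the point. It does not justify a rule that makes the descriptive table depend on attribution.

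A third reply is that ungraded does not mean unrecoverable. The CRF is not shown and may carry a severity field for every AE, and source records might allow some later grading. That is fair: the claim is only about the data the protocol specifies.

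A fourth reply is that the concern about known allocation applies to one arm, since probiotic and placebo capsules are identical. A reader might go further and infer, from the local prescription for probiotic or placebo in section 4, that causality is judged with knowledge of all three arms. The text does not establish this; it does not say who is masked or how the prescription is coded.

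Finally, the opening sentence of section 13 can be read as loose wording, overridden by the all-AE rules after it. That is the likelier reading, so it is a matter of alignment and not evidence that unrelated events go unrecorded.

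**Conclusion.** The point holds within limits. Followed as written, the protocol requests no severity grade for AEs judged unrelated, so a between-arm comparison of moderate or severe AEs free of the causality judgement cannot be formed from protocol-specified data. The judgement may differ by arm because one active treatment is an unmatched chewable tablet.

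The consequence is confined to the breakdown by severity; the primary and secondary endpoints and the all-cause AE counts are unaffected. Its numerical size is unknown. The conclusion assumes that the CRF follows the protocol and asks for nothing more. It does not require that attribution actually differs between arms, only that nothing prevents it. This is a cheap improvement worth making, not a flaw that threatens the trial's main conclusions.

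**What to change.** In section 13.5 (Assessment of severity), ask for the existing mild/moderate/severe grade for every AE in every arm, independently of the causality assessment. Reword the opening sentence of section 13 so that its scope matches the all-AE wording of 13.2 and 13.3.

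The cost is one extra eCRF field for AEs judged unrelated; the scale already exists and no treatment rule changes. The change removes the causality filter from the severity data. It does not remove the possible influence of known allocation on the grade itself, which should be acknowledged when severity is reported for the calcium/vitamin D arm.

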14. OVERSIGHT ARRANGEMENTS

14.1 Inspection of records

Investigators and institutions involved in the study will permit trial related monitoring and audits on behalf of the sponsor, REC review, and regulatory inspection(s). In the event of audit or monitoring, the Investigator agrees to allow the representatives of the sponsor direct access to all study records and source documentation. In the event of regulatory inspection, the Investigator agrees to allow inspectors direct access to all study records and source documentation.

14.2 Study monitoring and audit

The ACCORD Sponsor Representative will assess the study to determine if an independent risk assessment is required. If required, the independent risk assessment will be carried out by the ACCORD Quality Assurance Group to determine if an audit should be performed before/during/after the study and, if so, at what frequency.

Risk assessment, if required, will determine if audit by the ACCORD QA group is required. Should audit be required, details will be captured in an audit plan. Audit of Investigator sites, study management activities and study collaborative units, facilities and 3rd parties may be performed.

15. GOOD CLINICAL PRACTICE

15.1 Ethical conduct

The study will be conducted in accordance with the principles of the International Conference on Harmonisation Tripartite Guideline for Good Clinical Practice (ICH GCP).

Before the study can commence, all required approvals will be obtained and any conditions of approvals will be met.

15.2 Investigator responsibilities

The investigator will be responsible for the overall conduct of the study at the site and compliance with the protocol and any protocol amendments. In accordance with the principles of ICH GCP, the following areas listed in this section are also the responsibility of the Investigator. Responsibilities may be delegated to an appropriate member of study site staff.

15.3 Informed Consent

The investigator will be responsible for ensuring informed consent is obtained before any protocol specific procedures are carried out. The decision of a participant to participate in clinical research is voluntary and should be based on a clear understanding of what is involved.

Participants will receive adequate oral and written information – appropriate Participant Information and Informed Consent Forms will be provided. An oral explanation to the participant will be performed by the Investigator or qualified delegated person which will cover all the elements specified in the Participant Information Sheet and Consent Form.

The participant will be given every opportunity to clarify any points they do not understand and, if necessary, ask for more information. The participant must be given sufficient time to consider the information provided. It should be emphasised that the participant may withdraw their consent to participate at any time without loss of benefits to which they otherwise would be entitled.

The Investigator or delegated member of the trial team and the participant will sign and date the Informed Consent Form(s) to confirm that consent has been obtained. The participant will receive a copy of this document and a copy filed in the Investigator Site File (ISF) and participant's medical notes (if applicable).

15.4 Study Site Staff

The Investigator must be familiar with the protocol and the study requirements. It is the Investigator's responsibility to ensure that all staff assisting with the study are adequately informed about the protocol and their trial related duties.

15.5 Data Recording

The Principal Investigator is responsible for the quality of the data recorded in the CRF at each Investigator Site.

15.6 Investigator Documentation

The Principal Investigator will ensure that the required documentation is available in local Investigator Site files ISFs.

15.7 GCP Training

For this study, researchers are encouraged to undertake GCP training in order to understand the principles of GCP. However, this is not a mandatory requirement. GCP training status for all investigators should be indicated in their respective CVs.

15.8 Confidentiality

All laboratory specimens, evaluation forms, reports, and other records must be identified in a manner designed to maintain participant confidentiality. All records must be kept in a secure storage area with limited access. Clinical information will not be released without the written permission of the participant. The Investigator and study site staff involved with this study may not disclose or use for any purpose other than performance of the study, any data, record, or other unpublished information, which is confidential or identifiable, and has been disclosed to those individuals for the purpose of the study. Prior written agreement from the sponsor or its designee must be obtained for the disclosure of any said confidential information to other parties.

15.9 Data Protection

All Investigators and study site staff involved with this study must comply with the requirements of the appropriate data protection legislation (including the General Data Protection Regulation and Data Protection Act) with regard to the collection, storage, processing and disclosure of personal information.

Computers used to collate the data will have limited access measures via user-names and passwords.

Published results will not contain any personal data and be of a form where individuals are not identified and re-identification is not likely to take place

16. STUDY CONDUCT RESPONSIBILITIES

16.1 Protocol amendments

Any changes in research activity, except those necessary to remove an apparent, immediate hazard to the participant in the case of an urgent safety measure, must be reviewed and approved by the Chief Investigator.

Amendments will be submitted to a sponsor representative for review and authorisation before being submitted in writing to the appropriate REC, and local R&D for approval prior to participants being enrolled into an amended protocol.

16.2 Management of protocol non-compliance

Prospective protocol deviations, (protocol waivers), will not be approved by the sponsors and therefore will not be implemented, except where necessary to eliminate an immediate hazard to study participants. If this necessitates a subsequent protocol amendment, this should be submitted to the REC, and local R&D for review and approval if appropriate.

Protocol deviations will be recorded in a protocol deviation log and logs will be submitted to the sponsors every 3 months. Each protocol violation will be reported to the sponsor within 3 days of becoming aware of the violation. All protocol deviation logs and violation forms should be emailed to [contact]

Deviations and violations are non-compliance events discovered after the event has occurred. Deviation logs will be maintained for each site in multi-centre studies. An alternative frequency of deviation log submission to the sponsors may be agreed in writing with the sponsors.

16.3 Serious breach requirements

A serious breach is a breach which is likely to effect to a significant degree:

- (a) the safety or physical or mental integrity of the participants of the trial; or
- (b) the scientific value of the trial.

If a potential serious breach is identified by the Chief investigator, Principal Investigator or delegates, the co-sponsors ([contact]) must be notified within 24 hours. It is the responsibility of the co-sponsors to assess the impact of the breach on the scientific value of the trial, to determine whether the incident constitutes a serious breach and report to research ethics committees as necessary.

16.4 Study record retention

All study documentation will be kept for a minimum of 3 years from the protocol defined end of study point. When the minimum retention period has elapsed, study documentation will not be destroyed without permission from the sponsor.

16.5 End of study

The end of study is defined as the last participant's last visit.

The Investigators or the co-sponsor(s) have the right at any time to terminate the study for clinical or administrative reasons.

The end of the study will be reported to the REC, and R+D Office(s) and co-sponsors within 90 days, or 15 days if the study is terminated prematurely. The Investigators will inform participants of the premature study closure and ensure that the appropriate follow up is arranged for all participants involved. End of study notification will be reported to the co-sponsors via email to [contact]

A summary report of the study will be provided to the REC within 1 year of the end of the study.

16.6 Continuation of treatment following the end of study

Not applicable for this study

16.7 Insurance and indemnity

The co-sponsors are responsible for ensuring proper provision has been made for insurance or indemnity to cover their liability and the liability of the Chief Investigator and staff.

The following arrangements are in place to fulfil the co-sponsors' responsibilities:

- The Protocol has been designed by the Chief Investigator and researchers employed by the University and collaborators. The University has insurance in place (which includes no-fault compensation) for negligent harm caused by poor protocol design by the Chief Investigator and researchers employed by the University.
- Sites participating in the study will be liable for clinical negligence and other negligent harm to individuals taking part in the study and covered by the duty of care owed to them by the sites concerned. The co-sponsors require individual sites participating in the study to arrange for their own insurance or indemnity in respect of these liabilities.
- Sites which are part of the United Kingdom's National Health Service will have the benefit of NHS Indemnity.
- Sites out with the United Kingdom will be responsible for arranging their own indemnity or insurance for their participation in the study, as well as for compliance with local law applicable to their participation in the study.

17. REPORTING, PUBLICATIONS AND NOTIFICATION OF RESULTS

17.1 Authorship policy

Authorship on the publications that result from this work will be determined on the basis of ICMJE recommendations which stipulate that authorship be based on the following 4 criteria:

- Substantial contributions to the conception or design of the work; or the acquisition, analysis, or interpretation of data for the work; AND
- Drafting the work or revising it critically for important intellectual content; AND
- Final approval of the version to be published; AND
- Agreement to be accountable for all aspects of the work in ensuring that questions related to the accuracy or integrity of any part of the work are appropriately investigated and resolved.

The contribution of Individuals who contribute to the study but do not qualify for authorship will be acknowledged in the publication.

